8.3 Guidelines-based Medical/Stroke Unit Care

All acute stroke subjects should receive the best standard of care according to national guidelines. The model will be the Canadian best practices guidelines for acute stroke care. These are very

similar to the guidelines of the American Stroke Association and the European Stroke Organization. All subjects are expected to be admitted to hospital as part of routine standard of care.

It is expected that all subjects will undergo a routine work-up for the mechanism of their stroke and be treated appropriately and definitively. This is critically important because subjects who have an excellent early recovery are at the highest risk of early recurrent stroke.²⁴ We wish to prevent recurrent stroke from confounding the 30-day and 90-day clinical outcome such that subject who are well at discharge remain that way for the duration of the 90-day follow-up period.

We expect the following preventive care. Relevant subject with atrial fibrillation should be anti-coagulated. Patients with symptomatic carotid artery stenosis should undergo carotid revascularization early and definitely within two weeks of stroke onset.²⁵ Risk factors, including hypertension, elevated cholesterol, diabetes mellitus, tobacco smoking, should be treated appropriately and aggressively according to current standards of care.

We expect subjects to receive adequate hydration to prevent renal complications. Patients will receive intravenous radio-contrast media for CTA for endovascular intervention. While these medications are generally extremely safe in stroke patients,²⁶ simple hydration can prevent renal complications, particularly among patients with baseline borderline renal function and among those with diabetes mellitus. Further, patients with ischemic stroke are generally slightly hypovolemic at baseline. We recommend use of intravenous normal saline (0.9% saline) infusion at 1.5 – 2.0 cc/kg/h until the subject is eating and drinking safely and well. Therefore, for the typical subject this will mean intravenous normal saline at 75-125 cc/h overnight only. We do not recommend the use of bicarbonate solutions or N-acetyl-cysteine solutions for renal protection.^{27,28} In general, the risk of nephrotoxicity from modern non-ionic, iso-osmolar radiocontrast media is extremely low.

For subjects that are disabled from their stroke and require a longer in-patient stay and/or rehabilitation, it is expected that they will receive standard stroke unit care to prevent complications. These include:

- Deep vein thrombosis (DVT) prophylaxis for subject who are bed-bound or primarily bed-bound
- Swallowing assessments and prevention of aspiration pneumonia
- Early mobilization and physiotherapy to prevent skin breakdown, pneumonia, DVT/pulmonary embolism beginning 24 hours after randomization
- Early diagnosis and treatment of fever

All subjects are expected to receive expert stroke unit care and then rehabilitation according to their clinical need.

In brief, it is expected that:

- 1) Patients who are appropriate candidates for intravenous thrombolytic therapy within 4.5 hours of defined stroke onset to get rapidly administered intravenous alteplase therapy.
- 2) All subjects should be managed urgently with attention to physiology. Airway, breathing and circulation (ABC) first. Fluids – usually normal saline - should be administered, as

most patients are slightly hypovolemic. BP should not be aggressively treated other than to guidelines to allow thrombolytic therapy.

- 3) All subjects should be managed on a stroke unit which should include early mobilization, early rehabilitation, DVT prophylaxis, swallowing assessment and prevention of aspiration pneumonia, nasogastric (NG) feeding as appropriate and delayed (up to four weeks) placement of percutaneous endoscopic gastrostomy (PEG) tubes in the uncommon instance that these are needed.
- 4) All subjects should receive ASA therapy (minimally) within the first 48 hours of stroke but after a day plus one brain image showing no evidence of major hemorrhage.
- 5) Patients should not receive intravenous unfractionated heparin.
- 6) All subjects should be thoroughly investigated to sort out the mechanism of stroke and appropriate stroke prevention strategies implemented. There is little use in working very hard on a technical and aggressive approach to acute stroke if it is to be undone on day +10 with a recurrent embolus because a subject has not been effectively treated for a preventable cause of stroke.
- 7) All subjects should have relevant and appropriate stroke rehabilitation therapy including physical, occupational and speech therapy.

In summary, it is expected that all subject should have excellent, guideline based stroke care through the full 90 days.

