8.2.1.1 Acute Carotid Artery Stenting

It is recommended that carotid artery stenting should not be undertaken acutely in order to avoid the need for dual antiplatelet agents. It is strongly recommended that neuro-interventionists tackle the intracranial occlusion primarily and only then consider the extracranial carotid artery. In some circumstances, carotid angioplasty, without stenting may be required with a planned return to the neuro-intervention suite 2-3 days later for definitive carotid management with stenting. It is recognized that carotid artery stenting may still be required in some circumstances. The use of carotid artery intervention (angioplasty with or without stenting) will be monitored and specific data collected.

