8.11 Evaluations Following Randomization

Vital signs will be completed pre- and post-dose and at 24 and 48 Hours, and Day 5. An ECG will be completed at 24 ± 12 Hours. Blood tests will be conducted at 24 ± 12 Hours including: CBC (hemoglobin, platelets and hematocrit), electrolytes (sodium, potassium, chloride), INR, aPTT, serum creatinine and serum glucose.

All subjects will undergo a follow-up brain MRI [including a minimum of axial DWI, gradient-echo (GRE), FLAIR] at 24 ± 12 Hours from the time of randomization. The 24-hour MR is considered a standard of care imaging procedure; if MR is unavailable, then NCCT is allowed.

All subjects will have a mRS scale scores evaluated at Day 5 or discharge, Day 30, and Day 90. Additionally, a pre-morbid (baseline) mRS will be collected and recorded on the 24h CRF page. All subjects will also undergo a NIHSS assessment at 2 Hours (end of the angiogram procedure), 24 and 48 Hours, and Day 5 or discharge, 30, and 90. The BI will be completed at Day 30 and 90 days. The EQ-5D-5L will be completed at Day 30 and 90 days.

Mortality and discharge disposition will be assessed at Day 5 or discharge. Mortality will also be assessed at Day 30 and 90. Then BNT, SNAP and MoCA will be conducted at Day 90.

SAEs will be collected through to Day 90. AEs and concomitant medications will be collected to Day 30. All time windows are calculated from the time of randomization (time '0').

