The only subject who typically will require intubation include those with paradoxical agitation associated with a Wernicke's aphasia, or those who develop respiratory compromise due to aspiration or other event arising after randomization.

Carotid artery stenting:

It is recommended as a guideline that carotid artery stenting is should not be done as part of the treatment in the study. Tandem occlusion of the extracranial carotid at the bifurcation associated with an M1-MCA occlusion is common. Patients with tandem occlusions are eligible for enrolment. The target lesion initially is the M1-MCA occlusion. Advance a catheter past the ICA lesion and deal with the M1-MCA first. Very often, in this process, the proximal ICA is open at the end of treating the M1-MCA because of the mechanical manipulation of the occlusive lesion at the carotid. What was initially a 99% stenosis is reduced to 60 or 70%.

At this point stop. Treat the subject with ASA per rectum (since they cannot swallow) and bring the subject back the following day to decide on whether subsequent procedures are necessary. It is simply not necessarily true that forward flow in the carotid is required to keep the M1-MCA open.

The major potential difficulty with leaving a carotid stent in place is the need for antiplatelet therapy, which will increase the chance of major symptomatic bleeding.

If, despite the above, the treating physician deems that a stent is required – either intracranially or at the carotid bifurcation because this action is in the patients' best interest, we recommend using ASA and clopidogrel rather intravenous abciximab or eptifibatide. Give ASA per rectum and as soon as possible give 600 mg clopidogrel per NG.

Use of IA medications:

Use of intra-arterial medication such as alteplase, abciximab, eptifibatide, tirofiban is not advised although nothing in this protocol forbids the use of any treatment that the treating physician deems to be in the subject's best interest. Any such medications will be noted in the CRF. Note that alteplase is not indicated for direct IA catheter delivery.

Number of Devices / GP2b3a Inhibitors / When to stop:

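### Protocol 8.3 puts ASA after a next-day scan for all subjects, but Appendix 1 gives rectal ASA around the procedure, with or without a stent, and neither states an exception

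*Protocol*

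**What the plan says.** **Protocol 8.3, item 4** of the closing list of expected care: "All subjects should receive ASA therapy (minimally) within the first 48 hours of stroke but after a day plus one brain image showing no evidence". What the image must exclude is major hemorrhage. The item covers every subject and makes no exception for carotid disease or carotid intervention.

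**Protocol Appendix 1, Carotid artery stenting, no-stent paragraphs.** The appendix confirms that these are trial subjects: "Patients with tandem occlusions are eligible for enrolment". It tells the operator to treat the M1-MCA first and remarks: "Very often, in this process, the proximal ICA is open at the end of treating the M1-MCA". The instruction that follows is: "At this point stop. Treat the subject with ASA per rectum (since they cannot swallow) and bring the subject back the following day". The purpose of the return is to decide whether anything more is needed.

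**Same heading, stent paragraph.** If the treating physician judges that an intracranial or carotid stent is required after all: "Give ASA per rectum and as soon as possible give 600 mg clopidogrel per NG".

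Neither Appendix 1 paragraph mentions a hemorrhage-excluding scan before ASA. Protocol 8.11 places the follow-up brain image "at 24 ± 12 Hours from the time of randomization".

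**The concern.** Item 4 makes ASA conditional on a scan. Appendix 1 gives ASA to some of the same subjects with no such condition and, in the no-stent case, before the subject is brought back the next day. A site with a tandem occlusion cannot follow both as written, and nothing tells it which text governs.

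The protocol itself treats antiplatelet exposure as a bleeding matter. Appendix 1 warns that the antiplatelet therapy a carotid stent requires raises the chance of major symptomatic bleeding. Section 8.2.1.1 advises against acute stenting in order to avoid dual antiplatelet agents. Section 6.1.4.1 defines symptomatic intracranial hemorrhage among its selected safety outcomes. Sites could reasonably divide on whether ASA is given before hemorrhage has been excluded.

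**Working it through.** The plan gives no figure to reproduce here. The check sets the texts side by side and then does a short timeline.

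**1. Do the texts cover the same subjects?** Yes. Item 4 is worded for all subjects, and Appendix 1 states that tandem occlusions are eligible.

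**2. When does Appendix 1 give ASA?** In the no-stent case, the point at which the operator stops is the end of the M1-MCA work, and the return is on the following day. ASA sits between the two in the order of instructions, so it falls on the procedure day. Appendix 1 gives no clock time; this follows from sequence only. The stent paragraph gives ASA without a time or a scan condition; its request for speed attaches to clopidogrel.

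**3. When does item 4 allow ASA?** The wording can be read as a day-plus-one image, or as one day elapsed plus one image. Either reading puts ASA after the procedure.

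**4. How far apart are they?** Inputs:
- Day 1 image: 24 ± 12 h from randomization (Protocol 8.11). Earliest 24 − 12 = 12 h; latest 24 + 12 = 36 h.
- Revascularization target: 90th percentile under 90 min from NCCT, median 75 min or less (Protocol 8.4). 90/60 = 1.5 h; 75/60 = 1.25 h.
- The NCCT is scored before randomization (Protocol 7.1), so a time counted from NCCT is an upper bound on the time counted from randomization.

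Minimum gap = earliest image − latest on-target end of M1-MCA work:
- at the 90-minute target: 12 − 1.5 = 10.5 h;
- at the 75-minute median target: 12 − 1.25 = 10.75 h.

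For an image at the end of the window and ASA at 1.5 h, the gap is 36 − 1.5 = 34.5 h.

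This assumes that the image in item 4 is the Day 1 image of 8.11, and that revascularization marks the end of the M1-MCA work. The targets are not observed times: section 4.7 notes that 90th-percentile times in the ESCAPE trial were well above such thresholds. Slower procedures narrow the gap, but ASA given when the operator stops would follow the earliest Day 1 image only if the procedure ended more than 12 h after randomization.

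**5. Does any other text reconcile them?** None found. Item 4 does not refer to Appendix 1, and Appendix 1 does not refer to item 4. Section 8.2.1 points to Appendix 1 as guidance on recommended approaches without giving it precedence. Section 8.2.1.1 does not mention ASA.

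**The case against.** The best defense is that neither text is a mandatory trial procedure. The list in 8.3 describes what is expected and uses should; Appendix 1 is titled as additional guidance, and its carotid advice is offered as a guideline. The appendix also says, in its paragraph on intra-arterial drugs, that the protocol does not bar treatment the physician believes is in the subject's interest. A specific note about a carotid lesion just manipulated is easily read as an exception to a general stroke-unit summary.

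The advisory status stands and limits the severity. The exception reading is plausible and may be what was meant, but the documents do not say so, and item 4 is worded without exception. If the implied exception is accepted, it has to be accepted for both Appendix 1 paragraphs, since the stent paragraph also gives ASA with no scan.

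Three stronger readings are tempting, and the documents do not support them:
- **A conflict over the return visit.** Section 8.2.1.1 speaks of angioplasty without stenting "with a planned return to the neuro-intervention suite 2-3 days later for definitive carotid management with stenting", whereas Appendix 1 has a next-day return. These are different situations. The first follows an angioplasty and has stenting planned; the second is a visit to decide whether more is needed. They are not contradictory.
- **Every tandem occlusion treated without a stent is affected.** The instruction to stop follows the remark that the proximal ICA is very often open by then. It does not clearly cover an ICA that stays closed or needs angioplasty.
- **A conflict specific to alteplase.** Neither ASA text distinguishes alteplase status, so a separate rule for it would be new clinical content, not a reconciliation.

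**Conclusion.** The inconsistency is real and internal to the protocol: an imaging-first rule for all subjects beside two Appendix 1 paragraphs that give rectal ASA without one. On target times the no-stent instruction precedes the earliest Day 1 image by at least about 10 hours. The order of events does not depend on those targets being met closely.

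The consequence is uneven management of subjects on a bleeding-relevant co-treatment. A reader might go further and infer bias in the NA-1 versus placebo comparison. The documents do not support that: allocation is 1:1 and blinded, and site is both a minimization variable and a covariate in the primary model. Variation between sites in ASA timing should therefore fall on both arms alike. The primary safety outcomes are SAEs and 90-day mortality, and SAP section 8 lists no separate analysis of symptomatic intracranial hemorrhage. Sample size, alpha and the primary analysis are untouched.

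The number of subjects concerned cannot be given. Appendix 1 calls tandem occlusion common but states no frequency, and the conclusion needs none. No view is taken here on which ASA timing is right.

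**What to change.** Reconcile Protocol 8.3 item 4 with both the no-stent and the stent paragraphs of Appendix 1. State explicitly, for each paragraph, whether it is an exception to the imaging-first rule or is subject to it, and add a cross-reference in each section to the other. The choice belongs to the sponsor's clinical leads.

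The cost is a few sentences of protocol wording and a note to sites. It needs no new data, visits or subjects, and no change to the SAP.

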8.4 Speed of Intervention

A key principle of the neuroprotective and endovascular intervention is that it must be both fast and safe. The target NCCT to revascularization time is the 90th percentile < 90 minutes and median at 75 minutes or less. Similarly, an interim measure will be the NCCT to groin puncture time at 90th percentile of <60 minutes and median at <45 minutes. This will be measured from the time of the first slice of the baseline/qualifying NCCT head done at the ESCAPE-NA1 centre. The target complication rate is less than 1%. The quality of intervention will be ensured by hand-selection of sites and only be approved by the executive committee after a site visit. All sites will be selected from the ESCAPE trialists. New sites must submit evidence within the two years prior to commencement of the trial that they can meet the 90-minute target of CT-to-recanalization time. For sites that participated in the ESCAPE trial, their trial data will constitute proof of capability of treatment. A principle of the evaluation of neuroprotection by NA-1 is that it should be implementable without significantly delaying the subject's access to reperfusion.

A key and critical component of the trial will be an ongoing quality assurance program to ensure that sites can meet these targets for endovascular intervention. Training will be undertaken at the sites and continued on a quarterly basis. Monitoring of interval times will be collated and provided to sites on a quarterly basis so that regular feedback might induce appropriately fast treatment processes. Sites that fail to meet these objectives in the trial will be dropped from the trial.

The sites will be assisted to achieve these targets.

8.5 Consent Process

Signed informed consent will be obtained prior to any protocol-specific procedures from the subject or legally authorized representative or, if required to enable inclusion by applicable

national laws and regulations and the applicable independent review boards/Ethics Committee requirements for obtaining consent, from the investigator after consultation with an independent physician who is not otherwise participating in the trial.

If the original process involved anyone other than the subject, and if required by local standards, consent will be sought for the remaining procedures from the subject once they are deemed to have regained capacity.

8.6 Baseline Clinical and Laboratory Evaluations

At Baseline, all subjects will undergo a routine neurological and clinical assessment (including history, examination and vital signs), the NIHSS and pre-stroke BI.

Emergency blood work will be drawn including: CBC (hemoglobin, platelets and hematocrit), electrolytes (sodium, potassium, chloride), INR, aPTT, serum creatinine and serum glucose. The study will use and collect local laboratory results and will not use a central lab. The results of this blood work are not required prior to randomization.

If the subject is female and is of childbearing potential a pregnancy test (urine point-of-care pregnancy test) must be completed and the result must be negative; this is the only mandatory laboratory test prior to randomization. Other laboratory or point-of-care testing may be performed at the discretion of the attending physicians and team.

An ECG should be completed at baseline. If the treating physician deems that a baseline ECG impedes the patient's access to timely care, the ECG must be performed within 6 hours of randomization.

All prior medications taken within three days of treatment initiation will be recorded on the e-CRF.

8.7 Immunogenicity Substudy

Plasma samples for immunogenicity analysis will be collected at Day 1 and Day 30 from up to 250 subjects enrolled at a subset of sites in Canada and the US.

8.7.1 Immunogenicity Sample Collection

At Day 1 (24 hours post dose – a time when no significant quantities of NA-1 remain in the blood) and Day 30 a 5 mL sample of blood will be collected in tubes provided by the Sponsor. Sample collection method should be the least invasive to the subject and may be combined with routine blood sampling.

The samples will be handled per guidelines/instructions provided by the sponsor. These tubes are labeled with adhesive labels that identify the study code, site number, the subject's number, and the sample Day. A minimum of 1.0 mL of plasma will be transferred into each cryovial.

The date and time for each step (blood draw, storage, centrifugation, aliquoting, and freezing) and the number of aliquots obtained must be documented in the source document.

8.7.2 Immunogenicity Sample Storage and Shipment

During storage, plasma tubes are to be kept in a freezer at -10°C or colder. The temperature will be monitored and documented for the duration of any sample storage.

Plasma will periodically be shipped frozen to the sponsor. Further shipping instructions will be provided by the Sponsor.

8.8 Pharmacokinetics Substudy

In order to assess Pharmacokinetics in the patient population, PK samples will be collected at baseline and at multiple time points after the complete dose was administered from up to 100 subjects enrolled at a subset of sites in Canada and the US.

8.8.1 PK Sample Collection

A total of six 2 mL blood samples for PK assessment will be drawn during the Baseline Visit. Time (T) =0 being the initiation of dosing of study drug or placebo. Samples will be drawn at the following timepoints:

- Sample 1: post randomization & prior to start of study drug administration (Time=0 min)
- Sample 2: 10 minutes from start of study drug administration (Time = 10 min)
- Sample 3: 20 minutes from start of study drug administration (Time = 20 min)
- Sample 4: 30 minutes from start of study drug administration (Time = 30 min)
- Sample 5: 60 minutes from start of study drug administration (Time = 60 min)
- Sample 6: 120 minutes from start of study drug administration (Time = 120 min)

At each timepoint a 2 mL sample of blood will be collected in tubes provided by the Sponsor. Sample collection method should be the least invasive to the subject and may be combined with routine blood sampling.

The samples will be handled per guidelines/instructions provided by the sponsor. These tubes are labeled with adhesive labels that identify the study code, site number, the subject's number, and the sample date and time. A minimum of 1.0 mL of plasma will be transferred into each cryovial.

The date and time for each step (blood draw, storage, centrifugation, aliquoting, and freezing) and the number of aliquots obtained must be documented in the source document.

8.8.2 PK Sample Storage and Shipment

During storage, PK tubes will be kept in a freezer at -10°C or colder. The temperature will be monitored and documented for the duration of any sample storage. PK samples will be stored in a separate cryobox from immunogenicity samples. All samples taken from the same subject should be stored in the same cryobox.

PK samples will be periodically shipped frozen to the Sponsor. Further shipping instructions will be provided by the Sponsor prior to study start up.

